recognized as a significant complication with the use of prophylaxis, particularly in R-/D+ patients (12-15). An evidence-based review showed that the incidence of CMV disease and specifically that of late-onset CMV disease in the valganciclovir era in these patients is substantially higher with prophylaxis than preemptive therapy (16). Overall, CMV disease has been documented in 2.6% of patients receiving preemptive therapy in the current era and in contrast to prophylaxis, it occurs largely within 100 days of transplantation (16). The frequency of CMV disease with prophylaxis and preemptive therapy based on studies in recent literature is summarized below. While, there are significant limitations of these data, including the fact that these are non-comparative studies and include heterogeneous transplant populations, there is a clear trend towards higher rates of CMV disease in patients who received prophylaxis compared to preemptive therapy.

CMV disease rates with antiviral prophylaxis for 3months						
Study	Sample size	Type of transplant	Drug	R/D status	Follow up	CMV disease (%)
(9)	177	Liver	VGCV	R-/D+	12 mo.	19
(17)	29	Liver	VGCV	R-/D+	12 mo.	30
(12)	38	Liver	OGCV	R-/D+	12 mo.	26
(2)	163	Kidney	VGCV	R-/D+	12 mo.	36.8
(18)	158	Kidney-panc	VGCV	R-/D+	12 mo.	39
(19)	25	Kidney	VGCV	R-/D+	12 mo.	40
(13)	67	Liver	OGCV/VGCV	R-/D+	12 mo.	28
(14)	54	Liver	VGCV	R-/D+	19mo.	26
(15)	39	Kidney	OGCV	R-/D+	12 mo.	31

CMV disease rates with preemptive therapy						
Study	Sample size	Type of transplant	Drug	R/D status	Follow up	CMV disease (%)
(20)	41	Liver	OGCV	R-/D+	4 mo.	0
(21)	22	Liver, Kidney	VGCV	R-/D+, R+	12 mo.	0
(22)	36	Liver	OGCV/ VGCV	R-/D+	20.4 pt/yr	0
(23)	42	Kidney, KP	VGCV	R-/D+	12 mo.	0
(24)	36	Liver	VGCV	R-/D+	62.8 pt/yr	0
(25)	11	Liver	VGCV	R-/D+	18 mo.	0
(26)	30	Liver	VGCV	All	12 mo.	0
(27)	36	Kidney	VGCV	R-/D+,R+	12mo.	5.5

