12.7.3 Immunologic endpoints [CMV-specific immunity]

12.7.3.1 T-cell immunity

Initial sample [100 days]: The proportions of subjects with detectable CMV specific monofunctional CD4+ and CD8+ T-cells (that produce IFN- γ) and CMV-specific multifunctional CD4+ and CD8+ T-cells (≥ 2 markers that include IFN- γ + additional cytokines such as IL-2 and TNF- α) will be compared between the two groups. It is hypothesized that T-cell immune responses will be greater in preemptive versus prophylaxis group and that positive responses will correlate with lack of development of CMV disease overall and late-onset CMV disease (69). A number of analyses will be carried out for these assessments. Proposed threshold levels that confer protection against CMV in transplant recipients are 0.4 CMV-specific T-cells/ μ l for both CD4+ and CD8+ T-cells (69). The percent of responders will be compared between the two treatment regimens using a Mann Whitney test.

The mean, median, range of multifunctional CD4+ and CD8+ T-cells will be summarized between the two regimens. The rate of CMV positive responders and the absolute number of CMV-specific T-cells will be compared between the subjects with adjudicated CMV disease and those without disease using GEE models. A receiver operator characteristic (ROC) will be used to estimate a cutoff for number of CMV-specific T-cells that appear to prevent the development of CMV disease.

Follow up samples [6 and 12 months] for immune assays will also be evaluated as above. In addition, a repeated measures model will be used to evaluate the relationship of each type of CMV response over time and the development of CMV disease.

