12.7.3.2 Neutralization antibody

This will be measured as titer of CMV neutralizing antibody [dilution factor]. Currently, the precise relationship between CMV neutralizing antibody and CMV disease is uncertain, therefore a number of exploratory analyses will be performed.

Initial sample [100 days]: The percent of samples demonstrating any detectable CMV neutralizing antibody will be compared between the two groups using a Chi square test. This activity will also be quantitatively evaluated. The titers will be transformed to a log10 and the log mean titers will be compared between the two groups using a t-test. A generalized estimating equation [GEE] regression model will be used to examine the relationship of antibody to CMV disease. The log transformed levels will be compared between a dichotomized grouping [subjects that develop CMV disease and those that remain disease free] using a t-test. The timing to onset of late CMV disease will also be compared between subjects with and without CMV antibody activity using a Kaplan-Meier probability estimate. The two probability functions will be compared using a rank sum test.

Follow up samples [6 and 12 months]: The follow up samples will be evaluated similarly to the initial sample. In addition, the log difference between the initial sample and the follow up sample will be calculated and compared between the two regimens using a regression analysis. A repeated measures model will be used to evaluate the relationship of CMV antibody activity over time and the development of CMV disease.

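### The exploratory immune-correlate analyses set no time order between sample and CMV disease, so disease before the sample can attenuate or reverse the association and the estimated protective cutoff

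*Combined protocol and SAP*

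**What the plan says.** Under the initial (100-day) sample, section 12.7.3.1 has responder rate and absolute T-cell count "compared between the subjects with adjudicated CMV disease and those without disease using GEE models". An ROC curve is then used to "estimate a cutoff for number of CMV-specific T-cells that appear to prevent the development of CMV disease". For the later draws: "Follow up samples [6 and 12 months] for immune assays will also be evaluated as above". A repeated-measures model of response over time against disease is added, also without a timing rule.

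Section 12.7.3.2 relates neutralizing antibody to disease by GEE, and compares log titers by t-test between "subjects that develop CMV disease and those that remain disease free". Follow-up antibody samples are handled similarly.

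Three passages bear on the other side. The T-cell hypothesis is that "positive responses will correlate with lack of development of CMV disease overall and late-onset CMV disease". An external threshold is stated in advance: "Proposed threshold levels that confer protection against CMV in transplant recipients are 0.4 CMV-specific T-cells" per µL, for both CD4+ and CD8+ cells. The antibody section also plans a Kaplan-Meier comparison of time to late CMV disease by antibody status.

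Samples are drawn at day 98, 6 months and 12 months, each ±14 days (7.6.2). The disease endpoint runs to 12 months post-transplant (3.2.1). Section 2.2.1 commits the study to finding protective thresholds.

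**The concern.** To say that a response level protects, the response must be measured before the disease. As written, a subject whose disease came before the blood draw counts as a case in the same way as one whose disease came after it.

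The protocol's own rationale makes this matter. Section 2.2 proposes that exposure to replicating virus primes CMV-specific cellular and humoral immunity, and CMV syndrome by definition requires detected virus (8.1.4.1). On that reasoning, disease before the sample can raise the measured response and pull cases towards or above the disease-free subjects.

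The share of earlier cases may also differ by arm. Section 2.2 says of disease under preemptive therapy that "it occurs largely within 100 days of transplantation", in contrast to prophylaxis. A pooled analysis could therefore mix timing effects with arm effects.

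A real immune correlate, which is the mechanism the trial proposes, could be hidden or appear with the wrong sign. A second, smaller issue is that the ROC cutoff is chosen and judged on the same few events with no planned correction.

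**Working it through.** **1. Timing rules.** The T-cell GEE and ROC text and the antibody GEE and t-test text contain no landmark, no exclusion or censoring of earlier cases and no time-dependent covariate. At the 12-month sample the disease window closes when the blood is drawn. Apart from the 14-day tolerance, no endpoint disease can follow it. The pilot's Figure 2 (section 2.2) did use the forward order, setting the 3-month response against late disease.

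**2. Number of events.** Section 12.1 gives 20 events and 160 subjects for 20% vs 5% disease. This reproduces with Freedman's log-rank formula:
- HR = ln(0.95)/ln(0.80) = 0.230
- events = (1.960 + 0.842)² × [(1 + 0.230)/(1 − 0.230)]² = 20.0
- N = 20.0/0.125 = 160

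By arm this is 80 × 0.20 = 16 prophylaxis and 80 × 0.05 = 4 preemptive events. At 176 subjects it is 88 × 0.20 + 88 × 0.05 = 22. Section 10.2 expects about 30 events for adjudication. The sample size is not in dispute.

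**3. Events before the day-100 sample.** The documents give no split. Assume 50–100% of preemptive events and 0–20% of prophylaxis events come first:
- low: 4 × 0.5 + 16 × 0 = 2 of 20 (10%)
- high: 4 × 1 + 16 × 0.2 = 7.2 of 20 (36%)

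About 13–18 events then follow the sample. By 6 months the earlier share also includes disease between day 100 and 6 months. By 12 months it is essentially all disease.

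**4. Effect on the association.** Assume a normal marker that is truly 0.8 SD lower before disease. The AUC (the probability that a case has the lower response) is Φ(0.8/√2) = 0.714. Assume a share s of cases predates the sample and that their responses sit b = 0 to 1 SD above the disease-free mean. Then

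AUC = (1 − s) × 0.714 + s × Φ(−b/√2), with Φ(0) = 0.50 and Φ(−0.707) = 0.24.

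| s | b = 0 | b = 1 |
|---|---|---|
| 0.10 | 0.69 | 0.67 |
| 0.35 | 0.64 | 0.55 |
| 0.50 | 0.61 | 0.48 |
| 1.00 | 0.50 | 0.24 |

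Simulation (3000 runs, 160 subjects, 20 events) agrees to within 0.01. The association weakens, then vanishes or reverses. The 0.8 SD separation, b and s are assumptions, not document figures.

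**5. Cutoff optimism, a separate matter.** The simulation places the cutoff at the best Youden index, with no earlier disease:
- No true effect, 20 events in 160: apparent 0.14, true 0.
- No true effect, 30 events in 176: apparent 0.12, true 0.
- True 0.8 SD, 20 events in 160: apparent 0.40, true 0.29 at the chosen cutoff. The cutoff itself has an SD of 0.43 (5–95% range −1.16 to +0.22 SD).

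**The case against.** A reader might infer that the protective threshold would be a product of reverse causation. The documents do not support that. If disease raises the response, earlier cases look better protected, so the bias works against a protective finding and cannot create one. A reader might also take the Youden figures as the size of the timing problem, but they measure only the optimism of a cutoff chosen on the same data.

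The rest of the defence has weight. The ROC sentence sits under the day-100 sample, and most planned events are in the prophylaxis arm, where section 2.2 describes a problem of late disease. Under the assumptions above, 64–90% of events would follow that sample. The hypothesis names late-onset disease, the antibody Kaplan-Meier analysis targets it, and 0.4 cells/µL is fixed in advance. Viremia without disease is part of the pathway under study, so only disease before the sample is a timing fault. Everything here is exploratory, and immune results do not affect subject care (7.6.2).

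These points limit the concern but do not remove it. The hypothesis covers overall disease as well, and neither the GEE nor the ROC sentence is limited to late onset. Late onset means after day 100 post-randomization (3.2.2), while the day-98 sample may be drawn up to day 98 + 14 = 112, so even that label does not guarantee the order. The Kaplan-Meier analysis covers antibody only. When follow-up antibody samples are handled the same way, late disease can again come before the draw. A pre-stated threshold does not validate a newly fitted one.

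**Conclusion.** The point holds as a gap in time order that can attenuate or reverse the relation between immune response and disease. It is probably modest at day 100: in the example, an AUC of 0.71 falls to between 0.69 and 0.55 when 10–35% of cases come first. It is larger at 6 months, though the documents do not allow that share to be calculated. At 12 months it is near total (AUC 0.50 to 0.24), and applying the same analysis there cannot be prospective. These sizes rest on the assumed separation, boost and early-case shares; the absence of a timing rule and the closing of the window at 12 months rest on the text alone. The lack of any planned validation of the ROC cutoff is a secondary weakness. No primary or secondary conclusion depends on these analyses, so this is a cheap improvement of low severity.

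**What to change.** Amend 12.7.3.1 and 12.7.3.2 as follows.

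- For the day-98/100 and 6-month samples, include only subjects free of CMV disease and still in follow-up on the actual sample date. Relate the response to disease with later onset, stratified or adjusted by arm.
- Apply the same ordering to the repeated-measures models.
- Use the 12-month sample descriptively only.
- Test the pre-stated 0.4 cells/µL threshold first. Report any new ROC cutoff with a confidence interval and bootstrap optimism-corrected sensitivity and specificity.

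No new data are needed. The cost is SAP wording, a little programming and fewer events: about 13–18 of 20 at day 100 under the stated assumptions, and fewer at 6 months. A 6-month cutoff may not be estimable, and the SAP should say that in that case the 6-month results will be summarised without one.

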12.7.3.2 Neutralization antibody

This will be measured as titer of CMV neutralizing antibody [dilution factor]. Currently, the precise relationship between CMV neutralizing antibody and CMV disease is uncertain, therefore a number of exploratory analyses will be performed.

Initial sample [100 days]: The percent of samples demonstrating any detectable CMV neutralizing antibody will be compared between the two groups using a Chi square test. This activity will also be quantitatively evaluated. The titers will be transformed to a log10 and the log mean titers will be compared between the two groups using a t-test. A generalized estimating equation [GEE] regression model will be used to examine the relationship of antibody to CMV disease. The log transformed levels will be compared between a dichotomized grouping [subjects that develop CMV disease and those that remain disease free] using a t-test. The timing to onset of late CMV disease will also be compared between subjects with and without CMV antibody activity using a Kaplan-Meier probability estimate. The two probability functions will be compared using a rank sum test.

Follow up samples [6 and 12 months]: The follow up samples will be evaluated similarly to the initial sample. In addition, the log difference between the initial sample and the follow up sample will be calculated and compared between the two regimens using a regression analysis. A repeated measures model will be used to evaluate the relationship of CMV antibody activity over time and the development of CMV disease.

12.7.4 Cost effectiveness analysis

CMV disease and the costs associated with treating it are estimated to add \$25,000 to \$50,000 to the cost of organ transplantation (70, 71). In addition to the direct effects of CMV disease, CMV in transplant recipients may contribute to an increased risk of rejection and opportunistic infection (OI). These events add a substantial economic burden to solid organ transplantation related to diagnosis, treatment and increased hospital length of stay. In addition to the economic considerations, CMV may also reduce graft and recipient survival. Treeage Pro 2009 [Treeage software, Williamstown, MA] will be used to develop a decision analysis model. The basic model will be similar in structure to those developed by Mauskopf et.al (72) for evaluating CMV in renal transplantation and Annemans et.al.(73) in liver transplantation. The tree will be utilized to estimate the costs associated with the 2 CMV intervention strategies, preemptive therapy and prophylaxis. Each strategy has the principle outcome of CMV disease, no disease. The disease state (CMV disease/no CMV disease) then transitions to 4 possible outcome states: rejection, OI, both rejection and OI, or no complications. Rejection can then transition to graft loss/no loss. Each outcome state terminates as alive/dead. Transition probabilities will be estimated post hoc. The model will allow for a range of sensitivity analyses

in which the parameter estimates can be varied [for example at the 10th and 90th percentile of the observed value].

Data already collected in this study will be used for cost effectiveness analyses. These include length of stay, drugs received for CMV prophylaxis/preemptive therapy, CMV disease, treatment for leukopenia, and other outcomes including rejection and retransplantation. Available data already captured will be used for the analyses; no additional items will be collected specifically for costs efficacy analyses. Cost estimates are obtained from average standard costs for drugs and procedures available in the literature. No site specific costs will be collected.

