12.6 Secondary outcome measures

12.6.1 Clinical outcomes

12.6.1.1 Incidence of late onset CMV disease [adjudicated]

The incidence of adjudicated CMV disease will be determined at the 3 and 12-month time points (late-onset CMV disease) using an analysis similar to that specified for the primary analysis of the primary endpoint and, in addition, will include separate subset analyses for CMV syndrome and CMV tissue invasive disease. The analysis will be a Cochran-Mantel-Haenszel test of the significance of the odds ratio, while controlling for the use of induction antibody therapy and renal dialysis. In addition potential prognostic factors, such as allograft rejection will be examined with a Cox proportional hazards model applied to the ITT and modified ITT populations. This analysis will be used to test the presence of a treatment effect while controlling for the various prognostic factors entered into the model. Results will be reported as the hazard ratio comparing two groups.

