12.7.4.1 Total costs

Cost effectiveness will be estimated comparing the costs for each regimen. A cost-effectiveness ratio will be calculated as [Costs associated with preemptive therapy- costs associated with prophylaxis]/Effect of preemptive therapy-effect prophylaxis therapy]. Where the costs are the total composite costs derived from the analysis tree and the effect is CMV disease free success.

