12.7.4.2 Cost utility analysis

A Cost-utility analysis will estimate the cost per quality-adjusted life-years (QALY). Quality of life will be estimated for possible outcomes where 0=death and 1=perfect health. The utility values will be estimated from the literature for patients with end stage liver disease and cirrhosis (74, 75). A fully functioning graft at one year, in a recipient with no major complications is estimated to have a utility value of about .83. Utility values for subjects with complications will be estimated from articles listed in the Cost-effectiveness analysis registry (76). Cost per QALY will be estimated for both regimens.

Cost utility analysis is based on estimated utilities found in the literature for items already collected such as retransplantation/disease/death. No additional data items will be collected.

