APPENDIX C: EXPECTED EVENTS FOR LIVER TRANSPLANT PATIENTS

Expected events for liver transplant patients: The following events are expected to occur with a reasonable frequency in the typical/expected clinical course of a patient following liver transplant:

- Hepatobiliary: Graft rejection, non-function of liver, delayed graft function, hepatic artery thrombosis, hepatic necrosis, liver abscess, biliary complications, biliary stricture or leak, biliary stenosis, cholecystitis, pancreatitis, liver failure, hepatic necrosis, viral hepatitis, graft versus host disease
- Surgical: Leaks (gastrointestinal, biliary or anastomotic), hemorrhage, tracheostomy, return to the operating room for surgery, retransplantation, vascular stenosis or thrombosis (inferior vena cava, portal vein), anastomotic problems, strictures, hernia, lymphocele, incision dehiscence, abdominal wall defect, wound infection, hernia, fluid collection, seroma, biloma, hematoma, abdominal wall defect, infarction of liver, vana caval tear
- Gastrointestinal: Nausea, vomiting, diarrhea, dyspepsia, abdominal distension or bloating, abdominal pain, anorexia, perforation, ischemic bowel, reflux gastritis, dyspepsia, ascites, ileus, bowel obstruction, GI bleed, achlasia
- Neurologic: Tremor, seizures, confusion, headache, dizziness, hallucinations, delusion, psychosis, insomnia, somnolence, lethargy, depressed level of consciousness, agitation, amnesia, anxiety, emotional lability, paralysis, vertigo, abnormal dreams, headache, cerebrovascular accident, subarachnoid hemorrhage, encephalopathy, posterior reversible encephalopathy syndrome, tacrolimus toxicity, progressive multifocal leukoencephalopathy, central pontine myelinolysis, neuropathy, abnormal vision, blindness, amblyopia, tinnitus, deafness
- Neuromuscular and skeletal: Hypertonia, incoordination, leg cramps, monoparesis, hemiparesis, myoclonus, nerve compression, quadriplegia
- Constitutional/ systemic : Fever, asthenia, failure to thrive, weight loss or weight gain, anasarca, embolism, multiorgan failure, malnutrition
- Infection: Fever, hypothermia, rigors, chills, systemic inflammatory response syndrome, infection (documented or suspected), sepsis, multisystem organ failure

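### The cost-effectiveness tree allows graft loss only after rejection, so a retransplantation without rejection has no branch to carry its cost or utility

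*Combined protocol and SAP*

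**What the plan says.** Section 12.7.4 describes one decision tree. Each strategy splits into CMV disease or no CMV disease, which "then transitions to 4 possible outcome states: rejection, OI, both rejection and OI, or no complications". The next sentence is the only one that brings in graft loss: "Rejection can then transition to graft loss/no loss". After that, "Each outcome state terminates as alive/dead".

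Section 12.7.4.1 makes this tree the source of the costs in the ratio: "Where the costs are the total composite costs derived from the analysis tree and the effect is CMV disease free success".

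Retransplantation is named as an input in two places, neither of which ties it to rejection. The data to be used in 12.7.4 include "other outcomes including rejection and retransplantation". In 12.7.4.2 the utilities come from the literature for "items already collected such as retransplantation/disease/death".

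In the clinical analyses, graft loss means retransplantation, dated by the retransplantation itself, with no condition on its cause (3.2.2, 12.6.1.5). Appendix C lists graft rejection among the expected hepatobiliary events and, as separate items, "non-function of liver, delayed graft function, hepatic artery thrombosis, hepatic necrosis". It lists retransplantation among the expected surgical events. Section 6.2.5 expects fewer than 2% of subjects to be retransplanted more than 30 days after randomization.

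**The concern.** The tree and its own input list do not fit together. Retransplantation is to be costed and given a utility, but the tree can receive it only from subjects who had rejection. A subject whose graft fails for another reason, such as non-function or hepatic artery thrombosis, ends in the OI or no-complications state. Both go directly to alive or dead, with no graft-loss node.

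The quantities at stake are the total cost of each regimen and its QALYs, both listed as exploratory endpoints in 3.2.3. Leaving out a cost lowers the total, and leaving out a utility loss raises the QALYs. For each regimen the two errors therefore push cost per QALY in the same direction, downward.

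**Working it through.** The plan states no figure on this point that could be reproduced. The check has three parts: list the paths of the tree, work out which results an omission reaches, and bound the number of subjects.

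**1. Paths in the tree as worded.** I take the rejection node to include the state of both rejection and OI, which the text implies but does not state.

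- Per strategy and CMV state, rejection gives 2 (graft loss or not) × 2 (alive or dead) = 4 paths. Both gives 4, OI gives 2 and no complications gives 2, so 12 in all.
- Total: 2 strategies × 2 CMV states × 12 = 48 terminal paths.
- Paths with graft loss: 2 × 2 × 2 states (rejection, both) × 2 (alive or dead) = 16.
- Paths with graft loss through OI or no complications: 0.

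If the rejection node did not cover the state of both, graft loss would be on 8 paths, and still on none through OI or no complications.

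**2. Which results are affected.** Let q be the proportion of an arm retransplanted without rejection, and C the cost of a retransplantation (not given in the documents).

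- Total cost per subject in an arm is understated by q × C. QALYs are overstated by the corresponding utility loss.
- The cost difference in 12.7.4.1 is off by (q in the preemptive arm − q in the prophylaxis arm) × C. It is zero if the two proportions are equal.
- The denominator of that ratio is CMV-disease-free success, which the missing branch does not touch.
- Section 12.7.4.2 plans a cost per QALY for both regimens. A figure for a single regimen carries the omission even when q is equal in the two arms.

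The plan itself gives a reason why q might differ. Section 12.7.4 says that CMV may reduce graft survival, and 2.2 cites worse graft survival with late-onset CMV in liver recipients. The design assumes CMV disease in 20% and 5% of the arms (12.1). If CMV disease leads to graft loss by a route other than rejection, the tree has no branch for it, and the omission would be larger in the arm with more CMV disease.

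**3. Number of subjects.** Expected number per arm = 88 × retransplantation rate × share without rejection, where 88 is half of the 176 target. The 2% rate is the protocol's ceiling after day 30. The 5% and 10% rates, standing for all retransplantations, and the 25–100% share are assumptions.

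| Rate | Share 25% | Share 100% |
|---|---|---|
| 2% | 0.44 | 1.76 |
| 5% | 1.1 | 4.4 |
| 10% | 2.2 | 8.8 |

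**The case against.** The strongest reply is that 12.7.4 only sketches a basic model patterned on published ones, with transition probabilities to be set later, and that naming retransplantation as an input shows the analysts mean to count it. That may be the intention. But this is the only tree specified, costs come from it, and the planned sensitivity analyses vary parameter values, which cannot supply a missing branch. Length of stay is also an input and might absorb part of the cost, but the plan does not say so. For retransplantations after day 30, section 7.8.2 stops most data collection at that point.

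It is also fair to say that few subjects are involved, that equal rates cancel in the cost difference, and that the endpoint is exploratory with no stopping decision resting on it. All of this stands and limits the weight of the point. Eligibility also screens out some early failures, since a subject retransplanted before randomization no longer meets the first-transplant criterion.

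A reader might infer more than the documents support:

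- **That retransplanted subjects would be scored at the utility of about .83.** Section 12.7.4.2 reserves that value for a working graft without major complications, so its wording excludes them. The gap is that the tree gives them no other place.
- **That the tree is wrong to put rejection after CMV disease**, because in 12.6.1.1 "potential prognostic factors, such as allograft rejection will be examined" in relation to CMV disease. With probabilities estimated separately in each arm, each rejection is counted once wherever its node sits, so arm totals do not change.
- **That a single omitted retransplantation could cancel the expected saving from less CMV disease.** This needs a retransplantation cost, which the documents do not give, and an imbalance between arms. It also ignores the 43% lower drug use expected in the preemptive arm (2.2.2). Nor do the documents rank retransplantation among outcomes by cost.

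**Conclusion.** The point holds as a structural inconsistency. Followed as written, the tree leaves retransplantations without rejection out of each regimen's total cost and QALYs. The incremental ratio is affected only to the extent that such events differ between arms, and the documents do not establish that they will.

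The size is probably small: about 0.4 to 1.8 subjects per arm at the protocol's ceiling of 2% after day 30, and more if earlier retransplantations, for which the protocol gives no rate, are common. No monetary size can be given from the documents. The conclusion assumes that some retransplantations occur without rejection. Appendix C makes this plausible but gives no frequency. The primary analysis and the clinical graft-loss analyses are not affected.

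**What to change.** In 12.7.4, let all four outcome states (rejection, OI, both, no complications) branch to graft loss or no loss, populated from the recorded retransplantations whatever their cause, and attach the retransplantation cost and utility to each graft-loss branch. Add one check: the number of graft losses in each arm of the tree must equal the number of retransplantations counted directly in that arm over the same period.

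This needs a change of wording in the plan and a few more branches. Retransplantations and their dates are already recorded for 12.6.1.5, so no new data are required. A matching subject-level check on mean cost is not proposed, because no site-specific costs are collected and little is recorded after a retransplantation beyond day 30. The downside is that some added branches will hold few subjects, so their probabilities will be imprecise. The change is best made before the transition probabilities are estimated.
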